### 9.3.2.1 Antimuscarinic Adverse Events

Antimuscarinic TEAEs are of interest as a common event in the drug class and will be summarized by preferred terms. The preferred terms for TEAEs considered antimuscarinic are as follows:

- Constipation
- Dry mouth
- Dysuria
- Worsening of urinary retention
- Worsening of narrow-angle glaucoma.

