## **6.2 Adverse Events**

Recorded adverse events will be mapped according to the MedDRA thesaurus by the data management CRO for this study, with Theravance review and approval of the mappings. BioClinica will use MedDRA, version 18.1.

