### **9.3.2 Adverse Events**

Adverse events will be coded to the preferred terms of the Medical Dictionary for Regulatory Activities (MedDRA®). Summaries will present by system organ class (SOC), preferred term (PT) and severity and/or relatedness, the frequency and percentage of subjects reporting each observed event.

A treatment-emergent adverse event (TEAE) will be defined as any AE that begins on or after the date of first dose of study drug up to the date of last dose of study drug plus 7 days in the follow-up period. AEs observed during the period from obtaining informed consent to the start of administration of study drug will be regarded separately from TEAEs. Treatment-limiting AEs are defined as any event that leads to permanent or temporary discontinuation from treatment.

Summary of adverse events will be dependent on adverse events observed. If no adverse events meeting a specific table are observed, the summary table will not be completed.

Blank summary tables will not be utilized. The following is the list of adverse event tables:

Overall:

- Overall Summary of Adverse Events

By preferred term:

- Treatment-emergent Adverse Events by SOC and PT
- Treatment-emergent Adverse Events by PT
- Treatment-emergent Adverse Events by SOC and PT occurring in more than 1% of Study population
- Treatment-emergent Adverse Events by SOC, PT and LABA Use

By severity:

- Treatment-emergent Adverse Events by SOC, PT and Severity
- Moderate or Severe Treatment-emergent Adverse Events by SOC and PT
- Serious Adverse Events
- Deaths during Study

By relatedness:

- Drug-Related Treatment-emergent Adverse Events by SOC and PT
- Drug-Related Treatment-emergent Adverse Events by SOC, PT and LABA Use
- Drug-Related Treatment-emergent Adverse Events by SOC, PT and Severity
- Moderate or Severe Drug-Related Treatment-emergent Adverse Events by SOC and PT
- Drug-related Serious Adverse Events

Other:

- Adverse Events Leading to Premature Study Drug Discontinuation
- Adverse Events Leading to Temporary Interruption of Study Drug

The overall summary of adverse events will include the following summary lines, any AE, moderate or severe AEs, moderate or severe AEs related to Study Drug, serious AEs, serious AEs related to Study Drug, AEs leading to discontinuation, AEs leading to interruption, deaths during Study.

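### The antimuscarinic TEAE term list names urinary retention and narrow-angle glaucoma only as worsening, so as written it omits new-onset cases

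*SAP*

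**What the plan says.** Section 9.3.2.1 sets the purpose and the unit of the summary: "Antimuscarinic TEAEs are of interest as a common event in the drug class and will be summarized by preferred terms". It then fixes the content: "The preferred terms for TEAEs considered antimuscarinic are as follows". Five entries come next. Constipation, dry mouth and dysuria stand as plain event names. The last two are "Worsening of urinary retention" and "Worsening of narrow-angle glaucoma". Neither condition appears without the qualifier in this list or elsewhere in the visible SAP.

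Three other statements bear on how the list works:

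- **Coding (Section 9.3.2):** "Adverse events will be coded to the preferred terms of the Medical Dictionary for Regulatory Activities". Section 6.2 adds that the data management vendor "will use MedDRA, version 18.1".
- **Treatment emergence (Section 9.3.2):** a TEAE "will be defined as any AE that begins on or after the date of first dose of study drug", up to 7 days after the last dose.
- **General tables (Section 9.3.2):** these include "Treatment-emergent Adverse Events by PT" and a table by SOC and PT, neither restricted to the antimuscarinic list.

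The list of appendices gives Appendix 2 a title covering coding logic for concomitant medications and for adverse events of interest. Its content is not visible. Section 9.3.2.1 does not refer to it. The visible text cites it for bronchodilator classes (Section 8.3) and medication groups (Section 9.3.5).

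**The concern.** A class-effect summary should pick up every treatment-emergent occurrence of the events it names. Here two of the five entries are limited by their wording to aggravation of an existing condition, while the other three carry no such limit. The SAP gives no reason for the difference.

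A subject with no history of urinary retention or narrow-angle glaucoma who develops it on treatment has a new event, not a worsening. That is as relevant to an antimuscarinic class effect as an aggravation, but the list as worded does not include it.

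What is at stake is agreement between tables in the same report. The general TEAE tables would show the case and the antimuscarinic table would not. A reader who relies on the class-effect table alone would see an incomplete count.

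**Working it through.** The point turns on wording. The plan gives no figure to reproduce, and no alpha, power, effect size or sample size enters. The check sets the provisions side by side.

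**Inputs**

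- The list in 9.3.2.1: 5 entries, 2 with the worsening qualifier, 5 − 2 = 3 without.
- Open or closed: it is introduced as the full set of terms, with no phrase allowing others. Where the SAP wants an open list it says so, as in Section 7.5 for major protocol deviations.
- The TEAE rule in 9.3.2: based on start date only, with no clause on worsening.
- The coding rule in 9.3.2 and 6.2: MedDRA preferred terms, version 18.1.

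**A new-onset case followed through the plan**

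1. A subject without prior urinary retention develops it after the first dose and within 7 days of the last dose. By start date it is a TEAE.
2. It is not a worsening, so it matches neither qualified entry. It is not constipation, dry mouth or dysuria. It matches 0 of the 5 entries.
3. It is therefore not counted in the antimuscarinic summary as written.
4. It is counted in the TEAE tables by SOC and PT and by PT.

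The same steps apply to narrow-angle glaucoma.

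**How a programmer could implement the list**

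| Implementation | New-onset case | Worsening case recorded as a TEAE | Agrees with 9.3.2.1 as written? |
|---|---|---|---|
| Apply the qualifier as a condition | Not counted | Counted | Yes, but the SAP gives no rule for telling the two apart in coded data |
| Exact match, if the qualified phrases are not preferred terms in version 18.1 | Not counted | Not counted | Literal, but both entries are empty |
| Exact match, if the qualified phrases are preferred terms | Not counted when coded to the plain condition | Counted when coded to the qualified term | Yes |
| Drop the qualifier and match the condition | Counted | Counted | No, departs from the text |

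Which phrases exist as preferred terms in version 18.1 cannot be settled from the SAP, so both exact-match possibilities are shown. In the three rows that keep the listed wording, a new-onset case is left out. The only row that counts it sets the wording aside.

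**Size.** The SAP states no expected number of these events, so no undercount can be calculated.

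**The case against.** The strongest reply is that the undercount is not demonstrated, for three reasons.

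**Appendix 2 may govern the table.** Its title covers adverse events of interest, and 9.3.2.1 is the one place in the visible SAP that describes a group of events in those terms. Content that cannot be seen should not be treated as absent. This stands as a limit on the consequence: if the appendix lists the unqualified terms, no case is missed. It does not rescue the wording of 9.3.2.1, which would then conflict with the appendix without citing it.

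**Selection is by coded term, not by prose.** The SAP describes no variable that separates new onset from worsening, so it has no mechanism for keeping one and dropping the other. The observation is fair, but it does not make the list usable. Matched literally, the qualified phrases either select only events coded to them or select nothing. Read loosely, they require the programmer to ignore part of the prespecified text.

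**The qualifier may be loose drafting, and little follows from it.** The intent may well be to count any occurrence, but the SAP does not say so. The general tables do show every case, and with about 200 subjects planned (Section 4) a discrepancy could be found by inspection. That argues for a low rating, not for leaving the list as it stands.

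**Conclusion.** The concern holds as a minor defect. Two of the five entries that define the antimuscarinic summary are worded so that a new-onset treatment-emergent case matches none of them. One descriptive safety table is affected. No case is lost from safety reporting overall, and no hypothesis test or efficacy result is touched.

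The conclusion rests on reading 9.3.2.1 as it stands, as a closed list applied in its own words. Confidence is medium because Appendix 2 is not visible. If it already holds unqualified terms, the undercount is zero and what remains is a mismatch between the section and its appendix.

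**What to change.** In Section 9.3.2.1, replace the two qualified entries with the coded preferred terms for urinary retention and narrow-angle glaucoma, taken from the MedDRA version named in Section 6.2 and without the qualifier. Any treatment-emergent occurrence, new or worsened, then counts.

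Make the list agree with Appendix 2. If the appendix already holds the coding logic for these events, a cross-reference to it should be added and the wording in 9.3.2.1 brought into line.

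The cost is one line of SAP text and an updated term list for programming. No new data are needed.

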### 9.3.3 Vital Signs

For each nominal time point, vital signs will be summarized in terms of observed values and changes from Baseline. Vital signs outliers will be flagged in the listing.

Table 8: Vital Signs Outlier Thresholds

Heart Rate (bpm)	Systolic Blood Pressure (mmHg)	Diastolic Blood Pressure (mmHg)
<40	<85	<45
>110	>160	>100

### 9.3.4 Medical History

Medical history collected at screening will be provided in a data listing and a summary table.

### 9.3.5 Prior and Concomitant Medications

Prior and concomitant Medications will be listed and summarized separately. Tables and listings will be provided for concomitant bronchodilators, concomitant corticosteroids, Concomitant NON-COPD medications, Post-treatment Bronchodilators. Coding logic for each group is in [Appendix 2](#).

## Appendix 1:

The figure consists of a 3x3 grid of bar charts. The first two columns have relatively short bars, while the third column has significantly taller bars. Each bar chart features a small black square at the top left and a larger black rectangle below it. The bars in the third column are much taller than those in the first two columns.

**Appendix 3:** [REDACTED]

[REDACTED]	[REDACTED]

## Appendix 4:

[REDACTED]	[REDACTED]	[REDACTED]

[REDACTED]	[REDACTED]	[REDACTED]

## Appendix 5:

A series of 12 horizontal black bars of varying lengths, decreasing from left to right. The bars are evenly spaced and have a consistent thickness. The lengths of the bars decrease in a regular, linear fashion from the first bar on the left to the last bar on the right.

## Appendix 6:

## Listings
